Appendix 1 shows the data flow for patient participants through the trial.

Statistical methods

The data from each trial will be analysed using a generalised linear mixed model framework standard for stepped-wedge cluster designs[16]. Data from each time point are considered a repeated cross-section given the difficulty linking observations between patients in different time periods. The primary outcomes are of two types: count data (the number of consultations by mode of delivery and the number of prescriptions) and a continuous score (the patient trust outcome). For the former we

specify the following log-linear model, for patient $i = 1, \dots, N$ in cluster $j = 1, \dots, J$ at time period $t = 1, \dots, T$ with number of events y_{ijt}^1 :

$$y_{ijt}^{(1)} \sim \text{Poisson}(\lambda_{ijt})$$

$$\lambda_{ijt} = N_{jt} \exp(\eta_{ijt}^{(1)})$$

where N_{jt} is the denominator population (i.e. the number of active patients in cluster j at time t) and η_{ijt} is the linear predictor. For the continuous outcome y_{ijt}^2 we specify:

$$y_{ijt}^{(2)} \sim N(\eta_{ijt}^{(2)}, \sigma^2)$$

The specification of the linear predictor in both models takes the form:

$$\eta_{ijt} = x'_{ijt}\beta + z'_{jt}\gamma + \delta D_{jt} + \alpha_j + \psi_{jt}$$

where x_{ijt} is a vector patient-level covariates, z_{jt} is a vector of cluster-level covariates, D_{jt} is an indicator equal to one if cluster j has the intervention at time t and zero otherwise, and $\alpha_j \sim N(0, \sigma_\alpha^2)$ and $\psi_{jt} \sim N(0, \sigma_\psi^2)$ are cluster, cluster-time and individual random effects respectively. The treatment effect of interest from the Poisson model is an incidence rate ratio, although we will also provide absolute treatment effects for context, and from the linear model we will report only absolute treatment effects.

Inference

All models will be estimated using restricted maximum likelihood using the R package lme4. We will report point estimates, confidence intervals, and p-values but not make any claims of “statistical significance” given recent strong arguments against doing so[17]. P-values will be based on the null hypotheses $H_0: \delta = 0$ versus the two-sided alternatives $H_1: \delta \neq 0$ in each of the models. Given there are multiple primary outcomes we will adjust reported p-values for multiple testing using a stepdown method, which provides an efficient means of controlling the family-wise error rate[18]. We will derive the exact distributions of the test statistics to perform the stepdown procedure using a permutation test approach, by re-randomising clusters to different sequences in the stepped-wedge design[19]. This method ensures appropriate control of the family-wise error rate and avoids potential biases resulting from small numbers of clusters.

Data management

Each country team will store consent forms and raw data on their own university secure password protected server or if paper-based, such as consent forms, in a locked filing cabinet. The data will be electronic in an email attachment, or a photo of a list, or entered into a survey software, on the REaCH Moodle or a digital recording. The exact nature of the raw data will depend on the available infrastructures of individual clusters and their geographical proximity to the university. Data will be translated as necessary and transcribed locally. We will ensure a confidentiality agreement is in place for all transcribers. Two members of the local country team (one unblinded) will have access to a list which links a patient identifier to their identity and their informed consent forms. For REaCH trainees this will be three people because the facilitators will also know their identity and have access to their Moodle data. These will remain stored locally throughout the trial and not leave the country.

In Tanzania, data will be stored virtually in a server at Commission for Science and Technology (COSTECH) [name]. Email: [contact] Research Registry Office [contact]

Physical data will be stored at St. Francis University College of Health and Allied Sciences, Ifakara Health Institute (IHI), [name].

In Nigeria, physical and electronic data will be stored at College of Medicine, University of Ibadan, University College Hospital Campus, [name].

To reduce data entry errors, range checks and other quality control measures will be put in place during database design. Data cleaning and validation will be done monthly.

Data transfer

Participant identifiable data will be transferred from the health facility to the university-based research team electronically or by telephone. Electronic transfer will be in the form of encrypted emails, online survey or photographs of paper lists sent via end-to-end encrypted WhatsApp from named recipient to named recipient. Once the photo or email has been downloaded onto the university secure server it will be deleted from the mobile device. All devices used will be password protected. Data will be pseudonymised once at the university with a local copy of patient identifiable data linked to pseudonym stored securely in locked filing cabinet.

Pseudonymised trial data will be transferred from health facility to local secure storage, electronically and finally onto a trial database hosted by the Clinical Trial Unit at the Medical School, University of Ibadan, Nigeria. Trial teams from Nigeria, Tanzania, Birmingham and KCL will have access to the database for the purpose of data input, cleaning, monitoring and analysis.

Process evaluation data will be transferred from local secure storage, electronically onto a secure storage area hosted by the Clinical Trial Unit at the Medical School, University of Ibadan, Nigeria. Evaluation teams from Warwick, Nigeria, Tanzania and KCL will have access to the data for the purposes of data entry, quality monitoring and analysis. All electronically stored research data will be both password protected and encrypted.

See uploaded participant data flow in Appendix 1 illustrating data flow and secure repositories.

Methods: Monitoring

Trial monitoring

We will develop a single Trial Steering Committee (TSC) to oversee both trials. Members will be drawn from the country networks, our broader collaborators in other LMIC and our existing project advisory groups for earlier projects [3,5]. The TSC will meet virtually on three occasions during the project life in months 3, 9 and 16. At each meeting a risk assessment paper will be completed and presented to the TSC for scrutiny and discussion.

Data monitoring

University of Ibadan will host an independent Data Monitoring and Ethics Committee (DMEC). The Committee comprises experienced researchers and community stakeholders and an independent statistician. The DMEC will liaise with the study statisticians at Birmingham and Ibadan to review unblinded patient safety data. The DMEC will meet during project months 2, 8 and 16 and report to the chair of the TSC. Interim analyses will be undertaken at trial month 6 specifically to monitor participant safety.

Harms

One unblinded co-investigator in each country will hold responsibility for monitoring prescriptions and investigation rates monthly by consultation type across all cluster data. Differences by consultation type of greater than 40% (i.e. equivalent to one visit per patient year) across each cluster will trigger a consideration of whether there could be a participant safety issue. Any such

difference will be investigated with the facility manager to identify and report any adverse or serious adverse events at an individual participant and/or cluster level. Where such events are revealed, this will be reported to the KCL PI, the country PIs and the chair of the DMEC.

Process evaluation

The process evaluation will a) explore patient and health-worker experience of remote consulting b) its impact on healthcare and c) enablers/impediments of remote consulting. It will be informed by:

1. MRC framework for complex intervention process evaluation [20] to understand how REaCH training impacts on health workers and in turn how remote consulting impacts healthcare experience.
2. TRAIN framework to assess how well the train-the-trainer approach works [9].
3. Consolidated implementation framework [21] to understand what enables/hinders implementation of remote consulting.

Participants and sampling

From all trial clusters we will collate data on the REaCH training: number and roles of tier 1 and tier 2 trainees, their sex, their engagement with each part of the training/cascading, and their text written during the REaCH training.

In all trial clusters we will survey facility managers and tier 1 trainees on implementation one month after completion of the REaCH training for the cluster. The timing allows them time to have reflected on the training and start planning delivery. The questionnaire provides the participant opportunity to reflect on implementation. We will collect information on how facilities distributed the airtime allowance across tier 1 and tier 2 trainees.

Observation, interview and prescription data will be collected in each country, from a random sample of five facilities (clusters) who receive the intervention during the first 6 months of the trial, to allow time for implementation prior to data collection.

Consent to process evaluation data collection will be taken along with consent to trial participation.

Training data (all clusters)

Prior to each REaCH training the facilitator will confirm consent to the use of aggregate data about the trainees/training and to the use of trainees' text for analysis in the study process evaluation clarifying that all personal identifiers will be removed before it is shared with the research team. This will be repeated at the end of the training. Trainees will be able to confidentially inform the facilitator if they do not wish their text to be included.

Survey of facility manager and trainees (all clusters)

All tier 1 trainees and the facility manager in all clusters will be invited to complete a questionnaire about implementation of remote consulting.

Observation (2x5 clusters)

We will observe two tier 1 and two tier 2 training sessions. Each REaCH facilitator will provide us with their timetable for training delivery. We will take a stratified random sample of planned training sessions to ensure observation of the range of modules within the training. Where individuals scheduled to attend observed training sessions have not given consent to be observed we will discuss with them their options. They may choose to attend but remain silent or they may choose not to attend. They will be offered a briefing session with the facilitator after the session so they are able to catch up on learning.

Semi-structured telephone interviews (2x5 clusters)

We will interview 3-4 months after training

- the facility manager
- the REaCH facilitator
- two tier 1 and two tier 2 health workers
- four patient trial participants

Within each cluster and each tier, from among health workers/patients consenting to participate in interviews will take a random sample.

Prescription data (2x5 clusters)

Prior to training and three months after training is complete, we will ask the facility managers to provide us with the timetable of sessions/clinics run at the facility including remote consulting, and identify those where prescriptions may be issued (e.g. we will exclude child immunisation sessions). We will stratify sessions/clinics by mostly remote consulting/mostly face to face and take a random sample of four sessions with a 1-2-week timeframe at each time point (prior to training and three months after training). We will collect prescription data on consecutive patients from each session.

Survey of facility manager and trainees

All tier 1 trainees and the facility manager in each cluster will be invited to complete three brief questionnaires 1) The four item Intervention Acceptability Measure (AIM), the four item Intervention Appropriateness Measure (IAM) and the four item Feasibility of Intervention Measure (FIM)[22]. We will aim to obtain a minimum of two completed questionnaires from each cluster. The REaCH facilitator will ask the tier 1 trainees for permission to give their name and phone number to the research team. Once informed consent is completed the researcher will ask the trainee to complete the four questions by paper, telephone or via email.

Data collection

All data will be collected via the internet or phone or using social distancing at primary care facilities. Appendix 4 contains a participant distress protocol for anyone feeling uncomfortable during an interview.

Training data

Data on number and roles of trainees and engagement with each part of the training/cascading will be collated by facilitators and passed to the research team as aggregate data. Facilitators will extract student text and remove identifiers before passing it to the research team.

Survey of facility managers and Tier 1 trainees

Four brief surveys will be used to assess the feasibility of implementation of remote consulting. The surveys are 1) The four item Intervention Acceptability Measure (AIM), the four item Intervention Appropriateness Measure (IAM) and the four item Feasibility of Intervention Measure (FIM)[22]. Items are measured on a 5-point Likert scale, Completely Disagree to Completely Agree. The REaCH facilitators will send a link to the questionnaire, in English, to all participants one month after the training completion. Where necessary, in discussion with the facilitator, we will consider other approaches to this data collection including paper questionnaires and email. Survey data will be given a study ID with only the facilitator knowing which ID corresponds to which facility manager/trainee. The research team will be informed of whether the ID corresponds to a facility manager or trainee, whether the participant received REaCH training and in which three-month timeframe the training was received.

Observation

The researcher will be a non-participant observer, listening to discussion and reading posts related to the session. They will take field notes throughout the session. The fieldnotes will follow the sequence

of the session and note what is discussed, who participates in the discussion, and how the participants relate to each other in narrative form. Field notes will not include any identifiers. At the start of every observation we will remind participants about the study and verbally confirm consent.

Interviews

At the start of every interview we will remind participants about the study and verbally confirm consent. Interviews will be audio-recorded and transcribed/translated into English. All identifiers will be removed during transcription/translation. Transcripts will be checked against audio-recordings and then the audio-recording will be destroyed. All data will be labelled with a study ID.

District/facility manager and health workers

We will explore the experience of REaCH training, support and cascade and of undertaking remote consulting, how they have deployed remote healthcare themselves and within the facility, what impact this has on their working patterns, facility organisation and the experience of patients, what is working or not and why, and changes needed or made to enable remote consulting (e.g. facility expenditure on airtime, phones, appointment system, guidelines, policy). We will use initial analysis of survey data to inform how we probe during interviews.

REaCH facilitators

We will explore the experience of REaCH training, support and cascade, their understanding of how their trainees planned to or have deployed remote healthcare, what worked well or not in the training and adaptations they made to the training in response to the need of their trainees. We will ask them what enables the Tier 1 trainees to cascade training successfully and what hinders this, and how this cascade fits within other team activities.

Patient trial participants

We will explore their experience of remote consulting and its impact on their healthcare including what is working or not and why, expenditure on airtime and changes needed or made to enable remote consulting.

Prescription data

We will work with each of the clinics on how we collect this to avoid disrupting the clinic and ensuring patient confidentiality. We aim to collect the drug details from each prescription issued in the sampled sessions. We expect this will involve taking a photograph, ensuring the patient's name is not included in the photograph. There may be a step where a carbon copy is made when the prescription is issued which is then photographed.

Analysis

Training data

Data on trainee engagement will be summarised using descriptive statistics. Trainee text data obtained from the Moodle will be uploaded into NVivo for data management. Meaningful chunks of data will be coded based on its content. Through team discussion we will identify themes related to our objectives and move these into a framework of themes [21, 23] and training cohort. We will undertake within cohort comparison and cross cohort comparison. We will pay attention to how trainees consider remote consulting and its implementation and, how they plan to problem solve. From comparing data from cohorts implementing earlier and later in the trial we will gain insights into what external changes impact on the trainee's approach to mobile consulting and its implementation.

Survey data

We will use descriptive statistics for analysis. Each section of the questionnaire will be analysed separately as they relate to different implementation constructs[22]. The mean score is calculated for

each section [24]. We will examine the variation of scores by a number of parameters including role of participant (facility manager/trainee), receipt of REaCH training or not and in which 3-month timeframe the REaCH training was received. This analysis will assist with interpretation of our trial results.

Observation and interview data

Data from each cluster will be analysed together, to enable comparison of account between different methods of data collection and between different types participants within the same setting. We will then undertake comparison between clusters including across countries.

Data will be uploaded into NVivo for data management. Meaningful chunks of data will be coded based on its content. Through team discussion we will identify themes related to our objectives and move these into a framework [21,23] of themes and participants for each cluster. We will undertake within cluster comparison and then cross cluster comparison. We will pay particular attention to impact on healthcare as this will assist with interpretation of our trial results, how challenges are problem-solved as this provides applied learning, and the barriers that demand organisational or policy change as we will take these to decision makers.

Ethics

Stakeholder engagement

Through ongoing projects [3,5], local project advisory groups in Nigeria, Tanzania, Kenya, Uganda, Bangladesh, Pakistan have met 3-4 monthly each comprising 6-10 representatives from marginalised communities in urban and rural settings including:

- community residents, leaders, local women's/disability group representatives
- local healthcare workers and managers in these communities
- local/national government departments, NGOs, academic/research institutions and commercial companies (e.g. mHealth service providers, mobile companies)

Advice actioned from Nigeria and Tanzania has been to recognise the importance of context, understand and seek to integrate plans with existing services; and explore reasons for failure as well as success.

Empirically we have undertaken fieldwork with >300 community residents, 60 health workers and 50 local/national decision-makers about the availability, use and perceptions of remote consulting, its impact on users/healthcare workers and potential to strengthen access to health care(4,7). Community members saw value in remote consulting for sensitive and long-term conditions/requiring chronic care but emphasised the importance of establishing trust and ensuring communication about wider treatment pathways.

We will continue to engage key beneficiaries through our project advisory groups and as part of our process evaluation. Partners include the East African Science and Technology Commission (EASTECO) and Society for Telemedicine and eHealth, (Nigeria). Through our participation in ministerial working groups and committees, we reach decision-making bodies such as Digital Health Nigeria; the Tanzanian Ministry of eHealth Working Group; Kenya National mHealth and eHealth forum; Uganda Health Information, Innovation and Research (HIIRE) Technical Working Group. We have applied to list our REaCH Training through the World Health Organization Digital Clearing House.

Ethics approval

As sponsor, King's College London will provide ethical approval initially and, in accord with good ethical practices in LMIC research [25], this will be followed by applications for approval to St

Frances University College of Health and Applied Sciences, Tanzania and University of Ibadan, Nigeria.

In Nigeria we will seek approval from:

Oyo State Health Research Ethics Review Committee
Oyo State Ministry of Health
Department of Planning, Research & Statistics
[name],
Ibadan, Nigeria.

In Tanzania we will seek approval from:

National Health Research Ethics Review Committee
National Institute for Medical Research
[name]
[name]
Dar es Salaam, Tanzania
[contact]
[contact]
Email: [contact] ; [contact]

Exemplar participant informed consent documentation can be found in Appendices 2 and 3. The project has been peer-reviewed by the UKRI/GCRF/Newton Fund funding panel prior to making an award.

Ethical Issues

Privacy and confidentiality

The intervention promotes remote health consultations by mobile phone or fixed communal landlines by both patient and health care worker. This presents issues of privacy for both parties when engaging in a confidential health communication. The REaCH intervention training covers the issue of privacy for both partners. Health workers are trained to both ensure that the conversation is confidential at their end of the phone call. They are also requested to ask the patient at the other end of the phone whether they are receiving the call in a sufficiently private place to meet their needs. Our process evaluation will seek to understand how this is experienced in reality for both partners and the stepped wedge design affords us the opportunity to strengthen messages around privacy if we detect concerns.

Sex-based equality

In Tanzania and Nigeria more men than women own a mobile phone. The difference in ownership differs by country and across Africa as a whole, the difference is 8% fewer women owning mobile phones [26]. The potential impact of this is that women may have less access to remote consultations. If they have less access they may travel to health centres for face to face health care which puts them and their health workers at risk. Whilst fewer women own a mobile phone the majority have access either to a family phone or a fixed landline in the community [27]. To ensure that our research does not disadvantage women we will monitor recruitment within each cluster by sex. Where we find a difference in the sex of participants of greater than 10% this will trigger an over sampling in the process evaluation of the sex least represented so that we can understand the issue for women. The stepped-wedge trial designs means that we can monitor this and make changes to our trial procedures as we deliver REaCH training to subsequent health facilities to try and understand and address any sex imbalance that we find. However, the breadth of women's phone use is also narrower. REaCH training is intended to result in people having a trustworthy and safe experience of remote consulting with health workers and such experience may expand women's often self-restricted use of mobile services in general [26].

Protocol amendments

Protocol amendments with ethical implications will be subject to approval by all three ethical committees approving the trial. The proposed protocol amendments will not be implemented without prior ethical approval.

Consent or assent

All participants will undertake an informed consent process with information provided in written and spoken local languages and consent recorded in writing or verbally audio-recorded.

Confidentiality

Each participant's personal details will be linked to their study identifier in an excel spreadsheet that five members of the investigator team will have access to. This document will be password protected and encrypted. Responsibility for managing this database will be held with the Ibadan Trial manager and the database will be held on a secure Ibadan server. All data collection and recording will be GDPR compliant.

Declaration of interests

All investigators will register any conflicts of interest with the KCL PI and the KCL Trial Manager.

Ancillary and post-trial care

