We propose four primary outcomes, detailed below, to test our research hypothesis. Multiple primary outcomes are recommended against by some guidance for cluster trials (e.g. CONSORT) [10] as it "incurs the problems of interpretation associated with multiplicity of analyses". However, we opt for multiple primary outcomes here as the intervention is multi-faceted and may affect different aspects of patient care and their interaction with the health system in different ways. Appropriate inferences about the functioning of REaCH cannot be made on the basis of any singular outcome. We ensure appropriate correction for multiple testing for all our test statistics (see Statistical methods). Furthermore, we will not be using 'statistical significance' to make inferences about the effectiveness or not of the intervention, given the importance of including the full range of qualitative and quantitative evidence to make conclusions about the effectiveness of REaCH, which also limits the risk of faulty inferences made through the use of multiple primary outcomes. Our unit of analysis for all outcomes is at the individual level.

Primary outcomes:

- 1) Trust in healthcare provider: Physician Humanistic Behaviour Questionnaire (PHBQ) [11] determines the degree to which healthcare providers communicate humanistically with their patients. Humanistic communications engender trust between the patient and the healthcare worker. The PHBQ has face and content validity with patients and health workers for assessing these behaviours during remote consultations [12].
- 2) Face to face consultation rate: the number of visits per month for the eligible patient population where the patient is seen in person by the consulting health worker.
- 3) Remote consultation rate: the number of visits per month for the eligible patient population conducted using a telephone.
- 4) Prescribing rate: the number of prescriptions issued and collected to the eligible patient population per month. This outcome is a proxy for patient safety as a change in this outcome is an indicator of changes in safety and confidence. The meaning and impacts of changes in this indicator will be explored in the process evaluation.

Secondary outcomes:

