|----------------|-------------------------|----------------------------------|-------------------------|----------------------|----------------------|

| | | | | detectable effect | detectable effect |
|--|--|-----------------------------|----------------------|--------------------------|--------------------------|
| Face to face consultation/prescription rate | 0.25 consults/prescriptions per person-month | All active patients (n=100) | Incidence rate ratio | 0.84 | 1.20 |
| Remote consultation rate | 0.02 consults per person-month | All active patients (n=100) | Incidence rate ratio | 0.77 | 1.56 |
| Patient trust | 3.5 (sd=0.5) | Sampled patients (n=20) | Absolute effect | -0.07 | 0.07 |

A change in either consultation rate of an equivalent of one visit per person-year is considered “clinically significant”, which is well outside our minimum detectable range. Similarly, we will be able to identify reasonably small changes (~0.15 standard deviations) in patient trustworthiness score, although we do not hypothesise a change in this outcome.

Patient participant recruitment and sampling

At the study commencement each cluster provides the study with a pseudonymised list of active patients, giving us a patient ID and the basic information, we need from each patient (age, sex and eligible diagnosis). At the clinic they will have a link to patient ID with the patient’s record but we will not have access to the patient personal data. This is the open cohort for each cluster.

Each month we collect from each clinic a record of the consultations conducted and prescriptions and investigations ordered by the clinic, all they need to provide is the number of visits by type, prescriptions, investigations and any other information we need linked to a patient ID (e.g. patient 1234 had one remote visit, 2 prescriptions). Any additional patients can join the open cohort if they become eligible during the trial period.

Using the information, the research team can calculate outcomes, remove patients that are no longer active/who default, and sample for participation in the trust and patient activation outcomes and the process evaluation interviews. We will return the list of sampled patient identification number to the clinic for them to contact the potential participant so the research team can commence the informed consent processes.

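### The Poisson model for consultation and prescribing counts is written for a single patient but carries the whole cluster's active population as its exposure

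*Protocol*

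**What the plan says.** Four statements in the Protocol bear on this.

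- **Unit of analysis.** Outcomes: "Our unit of analysis for all outcomes is at the individual level".
- **Response.** Statistical methods announces for the count outcomes that the authors "specify the following log-linear model, for patient" i in cluster j at time t. The linear predictor contains x_ijt, which "is a vector patient-level covariates".
- **Mean.** The same section sets λ_ijt = N_jt × exp(η_ijt), where N_jt "is the denominator population (i.e. the number of active patients in cluster" j at time t.
- **Reported effect.** "The treatment effect of interest from the Poisson model is an incidence rate ratio", that is, exp(δ).

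The cohort that supplies N_jt is open. Under Sample size, a patient leaves after more than five months without being seen. Under Patient participant recruitment and sampling, "Any additional patients can join the open cohort if they become eligible during the trial period". The sample-size table assumes 0.25 face-to-face consultations or prescriptions per person-month and 100 active patients per cluster.

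**The concern.** A population size is the right exposure when the response is the cluster's total for the month. Here the response is one patient's count, and each patient contributes one person-month. With N_jt in the mean of every patient row, the model has to shrink exp(η) by a factor of N_jt to fit the data, and whatever moves N_jt moves the fitted rate in the opposite direction.

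This would be harmless if cluster size were constant. It is not: patients enter and leave, and leaving depends on contact with the clinic, which the training is meant to change. If cohort size shifts when a cluster is trained, the shift enters δ with its sign reversed. Growth looks like a falling rate and shrinkage looks like a rising one.

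The equation serves face-to-face consultations, remote consultations and prescribing in both trials. Prescribing is the protocol's proxy for safety, so a distorted ratio there could create or hide a safety signal. An analyst who follows the text literally would pass log(N_jt) as an offset on patient rows and get no warning from the software. The planned permutation p-values would not protect against this, because the permuted statistic comes from the same model.

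**Working it through.** **Inputs.** Rate 0.25 per person-month, 100 active patients per cluster, 80% power, 5% type I error, ICC 0.05, CAC 0.8 (Sample size); two-sided tests (Inference); 20 clusters in 10 sequences (Allocation); 12 monthly data periods (Participant timeline). The value of k is not in the documents and is assumed.

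**1. The plan's own figure.** Take the residual variance on the log scale as 1/0.25 = 4 per person-month, so that sampling variance per cluster-month is 4/100 = 0.04. The between-cluster variance is (0.05/0.95) × 4 = 0.2105, split by the CAC into 0.8 × 0.2105 = 0.168 (cluster) and 0.2 × 0.2105 = 0.042 (cluster-month). With fixed period effects, generalised least squares gives SE(δ) = 0.0644. The detectable ratios are exp(±(1.960 + 0.842) × 0.0644) = 0.835 and 1.198, against 0.84 and 1.20 in the table. The figure reproduces, and it treats 0.25 as a rate per person-month.

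**2. What the printed mean implies.** If exp(η) is that rate, the model expects 100 × 0.25 = 25 visits per patient per month. To fit a true mean of 0.25 per patient, exp(η) must be 0.25/100 = 0.0025. So exp(η) in the printed patient-level model is not the rate on which the trial was sized.

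**3. Why the two forms cannot be combined.** With exposure 1 and no patient-level covariates, summing N_jt patient rows gives a cluster total with mean N_jt × exp(η), which is the valid totals model. With N_jt already in each row, the sum has mean N_jt² × exp(η): 100² × 0.25 = 2,500 instead of 25. The population has been counted twice.

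**4. Effect on the reported ratio.** Let r be the patient's rate, so exp(η) = r/N_jt. If training multiplies r by the true ratio and cohort size by k (net of any trend shared by all clusters), then

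reported IRR = true IRR / k.

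This was checked with simulated Poisson fits: 20 clusters, 12 periods, about 100 patients per cluster, rate 0.25, true IRR 1, cluster and period effects, 60 replicates.

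| k (assumed) | Closed form 1/k | Printed model, simulated | Correct exposure, simulated |
|---|---|---|---|
| 0.8 | 1.25 | 1.24 | 0.995 |
| 0.9 | 1.11 | 1.12 | 1.005 |
| 1.0 | 1.00 | 1.01 | 1.006 |
| 1.1 | 0.91 | 0.90 | 0.995 |
| 1.2 | 0.83 | 0.84 | 1.007 |

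At k = 1.2, a true ratio of 1.20 would be reported as 1.20/1.2 = 1.00.

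**5. Trends shared by all clusters.** With no training-related change, cohort growth of 1% or 2% per month gave 1.01 and 1.00 when period effects were fitted, and 0.94 and 0.89 when they were not. The printed predictor shows no explicit time term, although one could sit in z_jt.

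**The case against.** The best defence is that the authors meant a model for cluster-month totals. The Outcomes section defines the rates for the eligible population, N_jt is called a denominator, and the sample-size table uses all active patients as its denominator. Step 1 of the check reproduces the table on exactly that footing. One predictor is printed for both model types, and the trust model does need the patient index and x_ijt, so these may simply have been carried over. On that reading the model is sound and no bias arises. This is plausible and it stands as a statement of possible intent. It does not rescue the text, because it contradicts the patient index, the patient-level covariates and the unit-of-analysis statement. One side or the other must change.

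Three stronger readings are tempting, and the documents do not support them.

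- **That any change in cohort size biases the result.** Only change associated with training status does. Common trends cancel if period effects are fitted. Constant size differences between clusters go into α_j, where they inflate its variance but do not bias δ.
- **That the five-month rule by itself produces a spurious fall.** If visits are memoryless and rise by one per person-year (0.25 to 0.333 per month), the share of patients seen within five months grows by (1 − e^(−5 × 0.333))/(1 − e^(−5 × 0.25)) = 0.811/0.713 = 1.137. A reader might turn this into a false ratio of 1/1.137 = 0.88 for that outcome. But the scenario presupposes a true rise. The rate per active patient goes up by 1.333/1.137 = 1.17, and the printed model would report about 1.17/1.137 = 1.03. That is attenuation, not a false fall. It also assumes random visit timing and prompt re-entry of lapsed patients, while the protocol describes attendance three times a year, roughly every four months if regular, which falls inside the window.
- **That the reported results will be biased.** That depends on how the model is coded and on a k that nobody has yet observed.

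**Conclusion.** The equation for three of the four primary outcomes is wrong as written, and the text needs correcting under either reading of its intent.

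The numerical consequence is conditional. It applies if the model is fitted to patient rows as printed and if cohort size changes with training. Over the assumed k of 0.8 to 1.2, a true ratio of 1 becomes 1.25 to 0.83. For face-to-face consultations and prescriptions, the upper end exceeds the detectable effect of 1.20 and the lower end sits at about the limit of 0.84. Against the redesigned Tanzania trial (0.81 and 1.23, Appendix 5), only the upper end lies outside. For remote consultations the same distortion is inside the wider range printed in the Sample size table (0.77 to 1.56).

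An open cohort whose membership depends on clinic contact means that k need not be 1, but the documents give no value for it.

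**What to change.** Choose one form for the count outcomes and state it before the analysis code is written.

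- **Patient rows.** Set λ_ijt = exp(η_ijt), with one row per active patient-month and exposure 1. Patients with no event in the month must be included. The monthly lists name only patients with events, so the zero rows have to be built from the cohort list that the research team already maintains. The unit-of-analysis statement stays as it is.
- **Cluster-month totals.** Define y_jt as the total for cluster j in month t, keep N_jt as exposure (offset log N_jt), remove x_ijt from the count model, and amend the unit-of-analysis statement in Outcomes for these three outcomes.

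Do not combine the two. In either form, say explicitly that period effects are in the predictor.

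The cost is a few lines of text. Monthly records are linked to patient IDs, so both forms remain open without new data or any change to the design.

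Neither form settles a separate matter: a rate per active patient uses a denominator that may itself respond to training. Reporting N_jt by month and training status would let readers judge that.
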